## Statistical Analysis Plan

Antev Ltd

Protocol Number: ANT-1111-02

Visit/ Procedure	Screeni ng	Treatment Period Groups 1 & 2												Follo w-up	Unsche d. Visit										
		Stage 1						Stage 2																	
Days/ Weeks		Da y 0	Da y 1	Da y 2	Da y 3	Da y 4	Da y 5	Da y 6	Da y 7	Da y 10	Da y 12	Da y 14	Da y 21	Da y 28	Da y 35	Da y 42	Da y 77	Da y 84	Da y 11	Da y 12	Da y 16	Da y 16	Da y 1	Da y 8	28 days after last dose
Visit Number	V1	V2	V3	V4	V5	V6	V7	V8	V9	V1	V1	V1	V1	V1	V1	V1	V1	V1	V1	V1	V1	V2	V21		
Window	D-6 To - 1	±0	±0	±0	±0	±0	±0	±0	±0	±1	±1	±1	±1	±1	±1	±1	±1	±3	±3	±3	±3	±3	±3 D		
Holter ECG (Group 2 only)	O	O																							
Safety Labs a	O	O															O	O	O	O	O	O			
Vital Signs	O	O															O	O	O	O	O	O			
Demograph hy b	O	O															O	O	O	O	O	O			
Injection of teverelix TFA IM c		O																							

Document:  
C:\ProgramData\activePDF\Temp\DocConverter\API\Input\\$651f4dc0b253\$FE3041C5883446E8  
92B20AB6D3F0E1BD.docx

Author: [name]

Version and Date: Version 1.0, 21 Apr 2023

Page 17 of 66

Confidential

## Statistical Analysis Plan

Antevs Ltd

Protocol Number: ANT-1111-02

Visit/ Procedure	Screeni ng	Treatment Period Groups 1 & 2												Follo w-up	Unsche d. Visit									
		Stage 1						Stage 2																
Days/ Weeks	Da y 0	Da y 1	Da y 2	Da y 3	Da y 4	Da y 5	Da y 6	Da y 7	Da y 10	Da y 12	Da y 14	Da y 21	Da y 28	Da y 35	Da y 42	Da y 77	Da y 84	Da y 11	Da y 12	Da y 16	Da y 16	Da y 1	Da y 8	
Visit Number	V1	V2	V3	V4	V5	V6	V7	V8	V9	V10	V11	V12	V13	V14	V15	V16	V17	V18	V19	V20	V21	V22	V23	
Window	D-6 To - 1	±0	±0	±0	±0	±0	±0	±0	±0	±0	±1	±1	±1	±1	±1	±1	±1	±1	±3	±3	±3	±3	±3	±3
Injection of teverelix TFA SC																								
Blood draw for pre- dosing local lab T testing																			○	○	○	○	○	○
PK/PD Blood Draw d																			○	○	○	○	○	○
PSA/hs PSA j																			○	○	○	○	○	○

Document:  
C:\ProgramData\activePDF\Temp\DocConverter\API\Input\\$651f4dc0b253\$FE3041C5883446E8  
92B20AB6D3F0E1BD.docx

Author: [name]

Version and Date: Version 1.0, 21 Apr 2023

Page 18 of 66

Confidential

**Statistical Analysis Plan**

Antev Ltd

Protocol Number: ANT-1111-02

Visit/ Procedure	Screeni ng	Treatment Period Groups 1 & 2												Follo w-up	Unsche d. Visit								
		Stage 1						Stage 2															
Days/ Weeks	Da y 0	Da y 1	Da y 2	Da y 3	Da y 4	Da y 5	Da y 6	Da y 7	Da y 10	Da y 12	Da y 14	Da y 21	Da y 28	Da y 35	Da y 42	Da y 77	Da y 84	Da y 11	Da y 12	Da y 16	Da y 16	Da y 1	Da y 8
Visit Number	V1	V2	V3	V4	V5	V6	V7	V8	V9	V1	V1	V1	V1	V1	V1	V1	V1	V1	V1	V1	V1	V2	V21
Window	D-6 To - 1	±0	±0	±0	±0	±0	±0	±0	0	1	2	3	4	5	6	7	8	9	9	9	0		
Cardiac biomarkers																							
Injection Site Inspection																							
Injection Site Photograph																							

Document:  
C:\ProgramData\activePDF\Temp\DocConverter\API\Input\\$651f4dc0b253\$FE3041C5883446E8  
92B20AB6D3F0E1BD.docx  
Author: [name]  
Version and Date: Version 1.0, 21 Apr 2023

Page 19 of 66

Confidential

## Statistical Analysis Plan

Antev Ltd

Protocol Number: ANT-1111-02

Visit/ Procedure	Screeni ng	Treatment Period Groups 1 & 2												Follo w-up	Unsche d. Visit
		Stage 1						Stage 2							
Days/ Weeks		Da y 0	Da y 1	Da y 2	Da y 3	Da y 4	Da y 5	Da y 6	Da y 7	Da y 10	Da y 12	Da y 14	Da y 21	Da y 28	
Visit Number	V1	V2	V3	V4	V5	V6	V7	V8	V9	V1	V1	V1	V1	V1	V1
Window	D-6 To - 1	±0	±0	±0	±0	±0	±0	±1	±1	±1	±1	±1	±1	±3	±3
Prior and current Concomita nt Medication s	O	O	O	O	O	O	O	O	O	O	O	O	O	O	O
Adverse Events	O	O	O	O	O	O	O	O	O	O	O	O	O	O	O

BMI=body mass index; D= days; ECG= electrocardiogram; hs=high-sensitivity; IM= intramuscular; PK= pharmacokinetic; PD= pharmacodynamic; PSA= prostate-specific antigen; SC= subcutaneous; T= testosterone.

a Safety laboratory tests are detailed in Section 4.2.6.

b Demographic details include height, weight, year of birth and age; During baseline and other visits including follow up (28 days after last dose) height, weight and BMI only will be measured.

Document:  
C:\ProgramData\activePDF\Temp\DocConverter\API\Input\\$651f4dc0b253\$FE3041C5883446E8  
92B20AB6D3F0E1BD.docx

Author: [name]

Version and Date: Version 1.0, 21 Apr 2023

Page 20 of 66

Confidential

## Statistical Analysis Plan

Antevs Ltd

Protocol Number: ANT-1111-02

c IM injection and SC injection of teverelix TFA will be given immediately sequentially (within 10 minutes of each other); IM first; all PK time points detailed relative to the IM injection time. Participants to be monitored for hypersensitivity reaction for 30 minutes following SC injection.

d On Day of dosing visit, blood samples for PK/PD analysis will be collected before the administration of the Maintenance Dose.

e Post-dose PK blood sampling on Day 0 is scheduled at the following time points: at 1, 1.5, 2, 2.5, 3, 4, 8, 12, 18 hours.

f Post-dose PK blood sampling at 24 hours. At the time point of 24 hours post-dose sampling for PD analysis (T, LH, FSH) will be initiated.

g Post-dose PK blood sampling at 48 hours.

h 72-hour PK profile: PD testing blood draw to be done at same time of day as the Day 0 pre-dose PK blood draw.

i PK and PD testing blood draw to be done at same time of day as pre-dose PK blood draw.

j If PSA is <0.06 ng/mL hs PSA will be measured and reported. If PSA is ≥0.06 ng/mL then hs PSA will not be measured and reported.

k If a visible injection site reaction is present, two photographs should be taken, and the better photograph uploaded to the eCRF

l ECGs to be done in triplicate at each visit

Document:  
C:\ProgramData\activePDF\Temp\DocConverter\API\Input\\$651f4dc0b253\$FE3041C5883446E8  
92B20AB6D3F0E1BD.docx

Author: [name]

Version and Date: Version 1.0, 21 Apr 2023

Page 21 of 66

Confidential

**Table 6 Schedule of Assessments for Groups 2 (Subjects entered in Stage 3)**

## Document:

C:\ProgramData\activePDF\Temp\DocConverter\API\input\\$651f4dc0b253\$FE3041C583446E822B20AB6D3F0E1BD.docx

Author: [name]

/version and Date: Version 1.0, 21 Apr 2023

Page 22 of 66

Confidential

## Statistical Analysis Plan

Antev Ltd

Protocol Number: ANT-1111-02

## Quanticate

The Clinical Data Experts

Visit/ Procedure	Screeni ng	Treatment Period Groups 1 & 2 (with Stage 3 subjects only)												Stage e 3										
		Stage 1						Stage 2																
Days/ Weeks		Da y 0	Da y 1	Da y 2	Da y 3	Da y 4	Da y 5	Da y 6	Da y 7	Da y 10	Da y 12	Da y 14	Da y 21	Da y 28	Da y 35	Da y 42	Da y 77	Da y 84	Da y 11	Da y 12	Da y 16	Da y 16	Da y 203- Day 252	*Da y 252
Visit Number	V1	V2	V3	V4	V5	V6	V7	V8	V9	V1 0	V1 1	V1 2	V1 3	V1 4	V1 5	V1 6	V1 7	V1 8	V1 9	V1 0	V21 -	V28		
Window	D-6 To - 1	±0	±0	±0	±0	±0	±0	±0	±0	±1	±1	±1	±1	±1	±3	±3	±3	±3	±3	±3	±3	±3	±3 D	
12-Lead ECG l	○	○													○	○	○	○	○	○	○	○		
Holter ECG (Group 2 only)	○	○													○	○	○	○	○	○	○	○		
Safety Labs a	○	○													○	○	○	○	○	○	○	○		
Vital Signs	○	○													○	○	○	○	○	○	○	○		
Demograp hy b	○	○													○	○	○	○	○	○	○	○		

Document:  
C:\ProgramData\activePDF\Temp\DocConverter\API\Inputs\\$651f4dc0b253\$FE3041C5883446E8  
92B20AB6D3F0E1BD.docx  
Author: [name]  
Version and Date: Version 1.0, 21 Apr 2023

Page 23 of 66

Confidential

Statistical Analysis Plan

Antev Ltd

Protocol Number: ANT-1111-02

## Quanticate

---

---

The Clinical Data Experts

Document:  
C:\Program  
92B20AB6D

Author: [name]

Version and Date: Version 1.0, 21 Apr 2023

Page 24 of 66

Confidential

## Statistical Analysis Plan

Antev Ltd

Protocol Number: ANT-1111-02

Visit/ Procedure	Screeni ng	Treatment Period Groups 1 & 2 (with Stage 3 subjects only)												Stage e 3										
		Stage 1						Stage 2																
Days/ Weeks		Da y 0	Da y 1	Da y 2	Da y 3	Da y 4	Da y 5	Da y 6	Da y 7	Da y 10	Da y 12	Da y 14	Da y 21	Da y 28	Da y 35	Da y 42	Da y 77	Da y 84	Da y 11	Da y 12	Da y 16	Da y 16	Da y 203- Day 252	*Da y 252
Visit Number	V1	V2	V3	V4	V5	V6	V7	V8	V9	V1 0	V1 1	V1 2	V1 3	V1 4	V1 5	V1 6	V1 7	V1 8	V1 9	V1 0	V21 -	V21 V28		
Window	D-6 To - 1	±0	±0	±0	±0	±0	±0	±0	±0	±1	±1	±1	±1	±1	±3	±3	±3	±3	±3	±3	±3	±3	±3 D	
PK/PD Blood Draw d	O e	O f	O g	O h	O i	O j	O k	O l	O m	O n	O o	O p	O q	O r	O s	O t	O u	O v	O w	O x	O y	O z		
PSA/hS PSA j	O									O	O	O	O	O	O	O	O	O	O	O	O	O		
Cardiac biomarkers	O														O	O	O	O	O	O	O	O		
Injection Site Inspection	O	O	O	O	O	O	O	O	O	O	O	O	O	O	O	O	O	O	O	O	O	O		

Document:  
C:\ProgramData\activePDF\Temp\DocConverter\API\Input\\$651f4dc0b253\$FE3041C5883446E8  
92B20AB6D3F0E1BD.docx  
Author: [name]  
Version and Date: Version 1.0, 21 Apr 2023

Page 25 of 66

Confidential

Statistical Analysis Plan

Antev Ltd

Protocol Number: ANT-11111-02

## Quanticate

---

---

The Clinical Data Experts

---

## Document:

C:\ProgramData\activePDF\Temp\DocConverter\API\Input\\$651f4dc0b253\$FEE3041C5883446E8922B20AB6D3F0E1BD.docx

Author: [name]

/version and Date: Version 1.0, 21 Apr 2023

Page 26 of 66

Confidential

## Statistical Analysis Plan

Antev Ltd

Protocol Number: ANT-1111-02

a Safety laboratory tests are detailed in Section 4.2.6.

\* Subjects should attend on Day 203 and weekly Day 252 (or until total T (local lab) is > 1 ng/mL – whichever occurs first)

b Demographic details include height, weight, year of birth and age; During baseline and other visits including follow up (28 days after last dose) height, weight and BMI only will be measured.

c IM injection and SC injection of teverelix TFA will be given immediately sequentially (within 10 minutes of each other); IM first; all PK time points detailed relative to the IM injection time. Participants to be monitored for hypersensitivity reaction for 30 minutes following SC injection.

d On Day of dosing visit, blood samples for PK/PD analysis will be collected before the administration of the Maintenance Dose.

e Post-dose PK blood sampling on Day 0 is scheduled at the following time points: at 1, 1.5, 2, 2.5, 3, 4, 8, 12, 18 hours.

f Post-dose PK blood sampling at 24 hours. At the time point of 24 hours post-dose sampling for PD analysis (T, LH, FSH) will be initiated.

g Post-dose PK blood sampling at 48 hours.

h 72 hour PK profile: PD testing blood draw to be done at same time of day as the Day 0 pre-dose PK blood draw.

i PK and PD testing blood draw to be done at same time of day as pre-dose PK blood draw.

j If PSA is <0.06 ng/mL hs PSA will be measured and reported. If PSA is ≥0.06 ng/mL then hs PSA will not be measured and reported.

k If a visible injection site reaction is present, two photographs should be taken and the better photograph uploaded to the eCRF

l ECGs to be done in triplicate at each visit

Document:  
C:\ProgramData\activePDF\Temp\DocConverter\API\Input\\$651f4dc0b253\$FE3041C5883446E8  
92B20AB6D3F0E1BD.docx

Author: [name]

Version and Date: Version 1.0, 21 Apr 2023

Page 27 of 66

Confidential

### **3. Patient Analysis Sets**

#### **3.1 Analysis Populations**

The analysis sets of interest are:

- Screening Population
- Safety Population
- Intention-to-Treat (ITT) Analysis Set
- Non-missing Central Lab Serum T Record at Day 28 (Lab Serum T Day 28) Analysis Set
- Per Protocol (PP) analysis Set
- Pharmacokinetic (PK) Analysis Set

The primary analysis will be performed on the per protocol (PP) population. In addition, a sensitivity analysis will be prepared in the intention to treat (ITT) population. All efficacy assessments on the PP population will be repeated for the ITT population. See Section 6.8 for further details.

It is planned that a separate PK SAP will be developed to provide a detailed description of the PK analysis based on the Pharmacokinetic (PK) Analysis set. The current SAP will only present general information as per the study protocol. It should be noted that the Pharmacokinetic Analysis set presented in the current SAP is solely for general information purposes and will not be utilized for any analysis described in this document.

#### **3.2 Screening Population**

All participants who signed the ICF will be included in the screening population.

#### **3.3 Safety Population**

All participants who have received any dose of IMP will be included in the safety population.

#### **3.4 Intention-to-Treat (ITT) Analysis Set**

All participants included in the safety population and for whom the primary endpoint is evaluable will be included in the ITT analysis set. Participants for whom the primary efficacy measure is evaluable are those who have a non-missing central lab serum T record at Day 28.

#### **3.5 Non-missing Central Lab Serum T Record at Day 28 (Lab Serum T Day 28) Analysis Set**

All participants included ITT analysis set, except for patients who received concomitant medications and herbal supplements that could possibly affect T levels, will be included in the Lab Serum T Day 28 analysis set.

If at the time of analysis this population is the same as the ITT population the analysis is conducted on, then results will not be repeated where the same question has been asked for the ITT population.

#### **3.6 Pharmacokinetic (PK) Analysis Set**

The PK Analysis Set is defined as the subset of the Per protocol (PP) analysis set providing analysable samples to assess the pharmacokinetics of the active substance.

A PK profile for a subject may be excluded from the PK Analysis Set in the relevant period/on that sampling occasion if the subject:

---

Document:

C:\ProgramData\activePDF\Temp\DocConverter\API\Input\\$651f4dc0b253\$FE3041C5883446E892B20AB6D3F0E1BD.docx

Author: [name]

Version and Date: Version 1.0, 21 Apr 2023

Page 28 of 66

- did not receive active treatment (e.g. excluding samples taken pre-dose and following administration with Placebo) or the correct dose.
- did not provide analysable samples at more than 50% of planned time points in the PK profile (e.g. due to drop out or laboratory errors).

All PK analyses will be performed on the PK Analysis Set.

In addition, PK data may be flagged to be excluded from specific summaries if, for example, the derived parameters are considered unreliable.

### **3.7 Per Protocol (PP) Analysis Set**

All participants included in the ITT analysis set who complete the study without major protocol violation will be included in the PP analysis set. Participants with major protocol violations will be excluded.

Protocol Violations will be classified as either 'major' or 'minor' in collaboration with the Sponsor. The criteria for this assessment will be defined before database lock. Patient inclusion or exclusion from this population will be confirmed following data review and prior to database lock. Listings will be prepared to show the eligibility of all participants prior to database lock. These listings will be presented in a Data Review Meeting.

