SC=subcutaneous; T=testosterone; TFA=Trifluoroacetate For participants in Group 2, the following actions will be taken at the Day 28 visit based on the results of the locally analysed T level determined from the Day 21 visit:

[T] (ng/mL)	Action Taken	Dose Administered
≤2	Continue with Stage 2 of Group 2	No dose on Day 28. Maintenance dose of 180 mg SC teverelix TFA every 42 days
>2	Withdraw from study; safety follow-up visit on Day 28	None

SC=subcutaneous; T=testosterone; TFA=Trifluoroacetate

Day 35 Visit

On Day 35, local testing of T levels will be performed to guide decision making at the Day 42 visit. PK, total T, LH, FSH and PSA (total and high-sensitivity [hs]) samples will also be collected for central laboratory analysis.

Stage 2 Visits in Groups 1 and 2

Day 28 Visit

Stage 2 will start at the Day 28 visit. However, participants will receive their first maintenance dose at the Day 42 visit and participants will visit the clinic at Day 35 to provide a blood sample for local laboratory testing of T levels.

Blood samples for PK and PD analyses (T, LH, FSH, PSA), and fasted (≥8 hours) safety laboratory testing will be collected. Samples will also be collected for urine analysis. AE assessment, physical examination, triplicate 12-lead ECG and assessment of vital signs (including sitting blood pressure and heart rate) will be performed.

If, in the opinion of the investigator, no safety concerns exist, participants will be discharged from the centre.

Visits at Day 42, Day 84, Day 126, and Day 168

On Day 42 the first maintenance dose will be administered.

Before administration of the maintenance dose, blood samples for PK and PD analyses as well as fasted (≥8 hours) safety laboratory testing will be collected. Samples will also be collected for urine analysis. Pre-dose AE assessment (including ISR), physical examination, triplicate 12-lead ECG and assessment of vital signs (including sitting blood pressure and heart rate) will be performed.

Participants will attend the clinic 1 week before each maintenance dose is given (i.e. at Days 35, 77, 119 and 161) to provide a blood sample for local laboratory assessment of T levels. At the Day 35 visit (only) PK, total T, LH, FSH and PSA (total and hs) samples will also be collected for central laboratory analysis. Based on the results of the local analysis of T level from 7 days prior to the scheduled visit, participants will receive:

[T] (ng/mL)	Action Taken	Dose Administered

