4.3 Participant Withdrawal Criteria

Premature study termination for an individual participant should be taken into consideration under the following circumstances:

- An illness/AE occurs during the study that influences the use, or the assessment of, the investigational medication
- He/she requires a forbidden concomitant medication (see Section 5.8.1)
- Adequate cooperation is not guaranteed

Decisions concerning study termination for individual participants will be made in accordance with the Medical Lead of the study and the Sponsor.

Premature study termination for an individual participant is mandatory under the following circumstances:

- Lack of efficacy and progressive disease (e.g. T levels >2 ng/mL)
- Lost to follow-up (the participant did not show up for the examination and the study personnel were unable to contact the participant)
- Death of the participant

The study must be terminated for an individual participant if the participant withdraws his/her consent or it is, in the investigator's opinion, necessary from a medical point of view (e.g. allergic reactions to the study medication).

If possible, a complete final examination, as planned for the visit that takes place on Day 168, should be carried out and documented on the corresponding pages of the electronic case report form (eCRF) for all participants who stop taking part in the study. If possible, the participant will also be asked to return to the site for a safety follow-up visit 28 days after the last administration of teverelix TFA.

Although participants may withdraw from the study at any time without giving any reasons, efforts should be made to find out the cause and document it.

For follow-up of participants' withdrawal because of an AE please see Section 6.3.7.3.

ANT-1111-02, Teverelix TFA in Prostate Cancer

FINAL Version 5.0, 31 May 2022

Page 37 of 84

Participants who terminate the study prematurely will not be replaced.

For criteria concerning the termination of the whole study please refer to Section 7.3.2.

5 Study Treatments

The IMP to be tested in this study is teverelix TFA, which is administered on Day 0 as a loading dose, followed by a maintenance dose as per the schedule below.

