8.1.1 Analysis Populations

All participants who have received least 1 dose of study medication will be included in the safety analysis (safety population). The efficacy analysis will be performed on an "intention-to-treat (ITT)" basis and a "PP" basis (see definitions below). Participants with major protocol violations will be excluded from the latter. For this purpose, protocol violations that could interfere with the objectives of the study, incorrect concomitant medications or violation of the inclusion/exclusion criteria etc. will be assessed as 'minor' or 'major' in collaboration with the Sponsor. The criteria for this assessment will be defined before analysis. Listings will be prepared to show the eligibility of all participants. These listings will be presented in a Data Review Meeting.

Definition of Analysis Populations:

Population	Description
Screening	All participants who signed the ICF
population	
Safety	All participants who received any dose of the IMP
population	
Intention-to-	All participants included in the safety population for whom the primary
treat (ITT)	endpoint is evaluable
analysis set	•
Per protocol	All participants included in the ITT analysis set who complete the
(PP) analysis set	study without major protocol violation

The primary analysis will be performed on the PP analysis set. In addition, a sensitivity analysis will be performed using the ITT analysis set. All efficacy assessments on the PP analysis set will be repeated for the ITT analysis set.

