#### **4.1.1 Primary Efficacy Measure**

The primary efficacy measure is the proportion of subjects achieving castration with central lab serum T <0.5 ng/mL or 1.73 nmol/L at Day 28. The denominator is the number of subjects who have a non-missing central lab T record at Day 28 in the relevant population.

---

Document:

C:\ProgramData\activePDF\Temp\DocConverter\API\Input\\$651f4dc0b253\$FE3041C5883446E892B20AB6D3F0E1BD.docx

Author: [name]

Version and Date: Version 1.0, 21 Apr 2023

Page 29 of 66

The primary parameter analysis will be performed on the PP analysis set. In addition, a sensitivity analysis will be performed on the ITT analysis set.

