## 6.8 Efficacy Analyses

The efficacy endpoints will include collected and derived, continuous and categorical variables. Continuous variables will be summarised as detailed in Section 5.1.2.

The primary analysis will be performed on the per-protocol (PP) population. In addition, a sensitivity analysis will be prepared in the intention-to-treat (ITT) population. All efficacy assessments on the PP population will be repeated for the ITT population.

The primary analysis is carried out on the PP population as there is no comparator and therefore no risk of bias towards one group. Also, due to the study design, it is not expected that there will be many protocol violations. Furthermore, it is not preferable for subjects who fail to attend the Day 28 visit to get their test to be included as non-responders in the primary response rate. If the response rate is below 90% in the ITT population but above in the PP, this will be considered in the interpretation of the results.

The following SAS code chooses the exact/Clopper-Pearson CI for the proportion of responders with two possible ways of extracting the data.

```
ods output binomialcls=<data out1>;
proc freq data=<data in> order= formatted; /* choose the correct order
option to specify which is the responder. See SAS documentation for
further details if required */
  table <responder variable> / bin(cl=exact);
  output out=<data out2>(keep=_bin_ xl_bin xu_bin) bin ;
run;
ods output close;
```

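### The primary Day 28 castration rate is analysed on a per-protocol set with an undefined study-completion condition, so read literally it depends on who is withdrawn, and the bias can go either way

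*SAP*

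**What the plan says.** Protocol 8.1.1 states: "The primary analysis will be performed on the PP analysis set". The ITT set is used for a sensitivity analysis. SAP 3.7 defines the primary set: "All participants included in the ITT analysis set who complete the study without major protocol violation will be included in the PP analysis set". Protocol 8.1.1 has the same rule, so completion is a condition separate from the absence of a major violation.

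SAP 4.1.1 sets the denominator: "The denominator is the number of subjects who have a non-missing central lab T record at Day 28 in the relevant population". For the primary analysis the relevant population is PP. ITT membership (SAP 3.4) needs only a dose and a Day 28 central T.

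For a Group 2 man whose Day 21 local T exceeds 2 ng/mL, the synopsis action is "Withdraw from study; safety follow-up visit on Day 28". Protocol 4.3 lists "Lack of efficacy and progressive disease (e.g. T levels >2 ng/mL" among the circumstances in which premature termination is mandatory.

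SAP 6.8 gives three reasons for making PP primary. The first is "The primary analysis is carried out on the PP population as there is no comparator and therefore no risk of bias towards one group". The second is that few protocol violations are expected. The third is that "it is not preferable for subjects who fail to attend the Day 28 visit to get their test to be included as non-responders". It adds that a response rate "below 90% in the ITT population but above in the PP, this will be considered in the interpretation of the results".

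**The concern.** A Day 28 response rate should be computed from the men whose Day 28 response was measured. The completion condition makes membership of the denominator depend on whether a man stayed in the study. One of the mandatory reasons for leaving is an earlier value of the same variable, testosterone. An observed Day 28 failure can then drop out of the primary analysis because treatment failed, and an observed Day 28 success can drop out because of something that happened months later.

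The Group 2 rate is judged against a 90% target and is meant to support Phase 3 dose selection (Protocol 8.1.12). A shift of a few men can move it across 90%, or move its lower limit across the 74.5% null.

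**Working it through.** **What completion means.** The documents point in different directions:

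- Protocol section 4 uses one PP set for response at Day 28 and up to Day 168.
- Protocol 8.1.12, in its Group 1 text, equates evaluable with having completed the Day 168 visit.
- The synopsis counts participants needed to complete the first 28 days.
- Protocol 8.1.10 runs the primary analysis once all participants have reached Day 28. A Day 168 condition could not yet be applied to everyone at that time.
- SAP 4.3.2 counts completed and prematurely withdrawn subjects separately, and gives no day for completion.

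**Do the SAP's reasons cover the completion condition?** The absence of a comparator rules out bias between arms, not bias in a single rate. The expected number of violations is beside the point, because withdrawal for T above 2 ng/mL follows the protocol. Missed Day 28 tests are already kept out by ITT membership, so the completion condition is not needed for that.

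**Design figures (Protocol 8.1.12).** Null 74.5%, alternative 90%, two-sided 5%, 50 evaluable, 80% power, 16% dropout, 60 recruited. With the normal approximation:

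- Power at n = 50 is Φ[(0.90 − 0.745 − 1.96·√(0.745·0.255/50)) / √(0.90·0.10/50)] = 0.79, in line with the stated 80%.
- 50/0.84 = 59.5, which rounds up to 60.
- The Clopper-Pearson interval for 54/60 is 79.5 to 96.2, matching the stated (79, 96).

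**Effect on one result.** If 51 of 60 men are castrate, the rate is 85.0% (95% CI 73.4 to 92.9). Removing four non-responders gives 51/56 = 91.1% (80.4 to 97.0). The estimate crosses 90% and the lower limit crosses 74.5%.

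**Losses of both kinds.** Start again from 51/60 and lose the planned 10 men, k of them non-responders. The rate becomes (51 − (10 − k))/50 = (41 + k)/50.

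| k | 0 | 1 | 2 | 3 | 4 | 5 |
|---|---|---|---|---|---|---|
| PP rate | 82.0% | 84.0% | 86.0% | 88.0% | 90.0% | 92.0% |

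The rate is unchanged when k/9 = (10 − k)/51, that is, k = 1.5. It falls for k of 0 or 1 and rises from k = 2.

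**Chance of clearing the null when the null is true.** Let R ~ Bin(60, 0.745) be the Day 28 responders, W ~ Bin(60 − R, f) the non-responders lost and L ~ Bin(R, g) the responders lost. The PP rate is (R − L)/(60 − W − L). Holding total loss at 16% gives g = (0.16 − 0.255f)/0.745. The probability is summed over outcomes with a Clopper-Pearson lower limit above 74.5% and W ≤ 6, because seven or more failures stop Group 2 (Protocol 3.1). The long-run PP rate is (0.84 − 0.255(1 − f))/0.84.

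| Non-responders lost (f) | Responders lost (g) | Long-run PP rate | Chance that lower limit > 74.5% |
|---|---|---|---|
| 0% | 0% | 74.5% | 1.7% |
| 10% | 18.1% | 72.7% | 0.8% |
| 16% | 16% | 74.5% | 1.6% |
| 25% | 12.9% | 77.2% | 4.0% |
| 30% | 11.2% | 78.8% | 6.0% |

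The first row has no loss at all. The values of f are assumptions, because the documents give only the 16% total.

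**The case against.** The literal reading is not the only one. If completion means the first 28 days, a man withdrawn at his Day 28 visit may count as a completer. Protocol 3.1 places the Group 1 withdrawal after Day 28. SAP 6.8 defends PP by expecting few violations, and the list of excluding deviations in SAP 4.3.3 does not mention withdrawal for high T. Both suggest that PP may have been meant as ITT minus violators. This stands as a limit on certainty: exclusion follows from the wording, but the documents do not settle that it was intended.

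The plan also limits the harm. All efficacy analyses are repeated on ITT. The Kaplan-Meier analysis in SAP 6.8.3 uses ITT and counts a man not castrate by Day 28 as an event. Readers of this uncontrolled, descriptive Phase 2 report will see both rates. That stands too, and it confines the defect to the PP-based primary estimate. It does not remove it, because a PP and ITT split around 90% is only to be considered in interpretation, with no rule for which estimate governs.

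A reader might infer that the rule always inflates the rate, or that it raises the false-positive chance to 4.1% or 9.5%. Those two figures arise if 10% or 25% of non-responders and no responders are removed, which does not match the planned 16% dropout. The withdrawal threshold (local T above 2 ng/mL at Day 21) is also four times the endpoint threshold (central T of 0.5 ng/mL at Day 28), and the documents do not say how many non-castrate men exceed it.

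Finally, a withdrawn man may lack a Day 28 central T. Protocol Table 9 schedules it and Protocol 7.2.4 includes pharmacodynamic sampling at follow-up, but the synopsis safety follow-up list names only safety assessments. Without the sample he is outside ITT as well.

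**Conclusion.** Wrong as written, and should be fixed. The primary Day 28 rate rests on a set whose completion condition is undefined. On its literal reading, the condition removes men with a measured Day 28 outcome because of withdrawal, partly driven by that outcome.

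The direction of the bias is not fixed. It is upward when non-responders are lost at a higher rate than responders, and downward when the reverse holds. At the planned total loss, the chance of wrongly clearing 74.5% runs from 0.8% to 6.0% over the assumed shares, against 1.7% with no removal. In single results the shift can carry the estimate across 90%.

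The documents do not support saying that withdrawn men certainly leave the denominator, that the bias is necessarily upward, or that the trial's other efficacy analyses are compromised. The size rests on the assumed loss shares and on withdrawn men having a Day 28 central T.

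**What to change.** For the Day 28 endpoint, delete the completion condition from the PP definition in SAP 3.7 and Protocol 8.1.1, and judge major violations only up to Day 28. Everyone otherwise eligible with a Day 28 central T then stays in. If a completer set is wanted for the Day 168 endpoints, define it separately and state which visit completes the study.

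As a sensitivity analysis only, count as non-responders the men withdrawn for T above 2 ng/mL on or before Day 28 who have no Day 28 central T. State this as an exception to SAP 5.3.1 (missing efficacy data not replaced), SAP 4.1.1 (non-missing denominator) and Protocol 8.1.6.

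The cost is wording in the SAP. If the protocol text is changed as well, Protocol 10.2 requires a formal amendment. No new data are needed, and the withdrawal rules are left as they are. The reported rate may move up or down.
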